5.4.2. Other Efficacy Measures

5.4.2.1. Patient Global Impression

The Patient Global Impression of Severity (PGI-S) will be collected at baseline (Visit 3) and monthly postbaseline visits during the double-blind treatment, open-label treatment, and post-treatment phase. In this single-item scale, patients rate the severity of their migraine condition on a scale ranging from "not at all ill" (coded as 1) to "extremely ill" (coded as 7).

The Patient Global Impression of Improvement (PGI-I) will be collected at monthly postbaseline visits during the treatment phase.

Change from baseline in PGI-S scores will be analyzed. Patient Global Impression of Improvement scores at postbaseline visits will be analyzed by adjusting for PGI-S score at baseline.

5.4.2.2. Non-Migraine Chronic Pain Assessment

The Lilly-developed non-migraine chronic pain assessment (questions shown below) will provide exploratory information on any changes in non-migraine chronic pain conditions that patients may be experiencing. The following questions are to be collected:

Q1: Does the subject have any non-migraine chronic pain conditions?

Yes

No

If Yes, go to Q2 and Q3.

Q2: What is the subject's chronic pain condition?

- AE Number:
- Medical History Number:

Q3: In the past week, what was the subject's average pain score related to this condition?

- 0 No Pain
- 1-9 where the patient would enter value of 1, 2, 3,..., up to 9, and the bigger the number, the worse the pain.
- 10 Worst pain imaginable

The average pain score of all non-migraine chronic pain conditions will be derived for each subject by averaging the pain scores of all reported non-migraine chronic pain conditions. The mean change from baseline in the average pain score will be used as analysis value.

If a specific non-migraine chronic pain condition is reported by more than 15% of the study population at baseline, the pain score of that specific condition will also be analyzed.

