To assess changes in efficacy, safety, and functional outcomes during Study Period IV (open-label treatment)	 In Study Period IV: Mean changes in all continuous measures of efficacy, safety, and functional outcomes that are also assessed in the double-blind period Among patients previously treated with LY2951742 who met 50% response criteria at Month 3 in the double-blind treatment period, the proportion of patients who demonstrate response for at least 6 of the 9 months in the open-label treatment period

Table CGAI.1. Objectives and Endpoints (continued)

Objectives (cont.)	Endpoints (cont.)
Other Secondary Objectives (cont.) To assess changes in efficacy outcomes during Study Period V as collected by electronic patient-reported outcomes (ePRO) diary data	In Study Period V: Changes in the number of monthly migraine and headache days from the baseline to the end of the post-treatment follow-up phase Time to first loss of response among patients who met 50% response criteria at their last injection interval Time to initiation of treatment with a migraine prevention medication
Tertiary Objectives	
CCI	
To explore the effect of LY2951742 on non- migraine chronic pain	Mean change from baseline in average pain severity of other chronic pain conditions
To compare LY2951742 with placebo with respect to categorical changes in quality of life	 Percentages of patients with: ≥50% improvement in MIDAS total score change from baseline in MSQ Role Function-Restrictive domain ≥10.9 change from baseline in MSQ Role Function-Preventive domain ≥8.3 change from baseline in MSQ Emotional Function domain ≥12.2
To compare LY2951742 with placebo with respect to the proportion of migraine headache days requiring medication for the acute treatment of migraine or headache	Change from baseline in the proportion of monthly migraine headache days requiring medication for the acute treatment of migraine or headache
To compare LY2951742 with placebo with respect to changes in symptomatology associated with migraine or probable migraine	 Change from baseline in the number of monthly migraine headache days with: nausea and/or vomiting photophobia and phonophobia aura prodromal symptoms other than aura

 Table CGAI.2.
 Migraine and Headache Endpoint Definitions

[figure not shown]
Diagnosis	Definition/Criteria	
Migraine headache	A headache, with or without aura, of ≥30 minutes duration which	
	meets criteria A and B or meets criterion C:	

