5.5.1.5. Baseline and Postbaseline Definition

Table CGAI.5.4 describes the rules for determining the patient population and baseline and postbaseline observations for each study phase and type of analysis. When "last of Visit x-x" is used in the table, the last nonmissing observation obtained in the visit interval will be used.

Table CGAI.5.4. Patient Population with Baseline and Postbaseline Definitions by Study Period and Type of Analysis

Study Period / Analysis	Patient Population	Baseline Observation	Postbaseline Observation(s)
Study Period III			
Efficacy analyses (Repeated Measures) or average of observed monthly values	ITT Population with a baseline and at least 1 postbaseline observation	Visit 3	All scheduled visits 3 < Visits ≤7
Efficacy analyses at LOCF endpoint		Visit 3	Last of Visit 3.01-7
Quality of Life analyses (Repeated Measures)		Visit 3	All scheduled visits 3 < Visits ≤7
Quality of Life analyses at LOCF endpoint or for average of observed monthly values		Visit 3	Last of Visit 3.01-7
TEAEs	Safety Population	All Visits 1–3	All Visits 3.01–7
Serious Adverse Events, Discontinuations due to Adverse Events	Safety Population	NA	All Visits 3.01–7
C-SSRS categorical analyses	Patients with a baseline and at least 1 postbaseline C-SSRS assessment	Recent History: Visits 1–3 excluding lifetime ^a All Prior History: Visits 1–3 including lifetime ^a	All Visits 3.01–7
Treatment-emergent abnormal laboratory values	Safety Population with normal laboratory values at all nonmissing baseline visits (with respect to direction being analyzed) and who have at least 1 postbaseline observation	Low: Minimum from Visits 1–3 High: Maximum from Visits 1–3 Abnormal: All Visits 1–3	Low: Minimum from Visits 3.01–7 High: Maximum from Visits 3.01–7 Abnormal: All Visits 1–3
Treatment-emergent immunogenicity	Safety Population	Visit 3	All Visits 3.01–7
Treatment-emergent changes in temperature and weight	Safety Population with a baseline and at least 1 postbaseline observation	Low: Minimum from Visits 1–3 High: Maximum from Visits 1–3	Low: Minimum from Visits 3.01–7 High: Maximum from Visits 3.01–7
Treatment-emergent changes in blood pressures, pulse, and ECGs	Safety Population with a baseline and at least 1 postbaseline observation	Low: Last non-missing from Visits 1–3 High: Last non-missing from Visits 1–3	Low: Minimum from Visits 3.01–7 High: Maximum from Visits 3.01–7

Patient Population with Baseline and Postbaseline Definitions by Study Period and Type of Analysis

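### The chronic pain score (SAP 5.4.2.2) does not fix which conditions are averaged: a new mild pain counts as improvement, and relief can be mis-scored or lost

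*SAP*

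**What the plan says.** The protocol's tertiary objectives (Table CGAI.1) include exploring the drug's effect on non-migraine chronic pain. The endpoint is "Mean change from baseline in average pain severity of other chronic pain conditions".

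SAP 5.4.2.2 gives the form and the derivation:

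- The first item is "Q1: Does the subject have any non-migraine chronic pain conditions", answered Yes or No. The branching instruction is "If Yes, go to Q2 and Q3".
- The second item identifies the condition by an AE number or a medical history number.
- The third is "Q3: In the past week, what was the subject's average pain score related to this condition", on a scale from 0 (no pain) to 10.
- The patient's score is formed "by averaging the pain scores of all reported non-migraine chronic pain conditions". Then: "The mean change from baseline in the average pain score will be used as analysis value".
- One supplement is planned. "If a specific non-migraine chronic pain condition is reported by more than 15% of the study population at baseline", that condition's score is analysed as well.

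In the protocol's Schedule of Activities (Appendix 2) the assessment falls at Visits 3, 7, 10 and 16 and at early termination, and a footnote says a clinician administers it. SAP Table CGAI.5.5 assigns ANCOVA for Study Period III and MMRM for Study Periods III/IV. Table CGAI.5.4 limits the Study Period III efficacy analyses to the "ITT Population with a baseline and at least 1 postbaseline observation".

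**The concern.** A change between two averages measures a change in pain only if both averages cover the same conditions. The SAP does not require that. It has no rule for a condition that appears after baseline, for one that is no longer listed, or for a patient who answers No to the opening question after having had a score at baseline.

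The SAP does settle such cases for other measures. Mean migraine severity is declared missing when there are no migraine headache days (SAP 5.4.1), and missing health care utilisation data become 0 under a stated condition (SAP 5.4.3.3). The pain score has no counterpart.

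At stake is whether the endpoint can answer its own exploratory question. The score can move in the opposite direction to the patient's pain, and some of the patients who respond most fully may contribute nothing to the double-blind comparison.

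**Working it through.** The plan gives no worked score, sample size or power for this endpoint, so there is no figure to reproduce. The rule is taken from SAP 5.4.2.2. The scores below are assumed for illustration.

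**Formulas.** Let a patient have k conditions with mean m at baseline, and let the pain of every other condition stay the same.

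- A new condition scored x is added: change as written = (x - m)/(k + 1). This is negative, so it counts as improvement, whenever x < m. On the baseline set the change is 0.
- A condition scored b resolves and is dropped from the report (k at least 2): change as written = (m - b)/(k - 1). This is positive, so it counts as worsening, whenever b < m. On the baseline set, with 0 for the resolved condition, the change is -b/k.

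**Results.**

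| Case | Baseline mean | Later mean | Change as written | Change on baseline set, resolved = 0 |
|---|---|---|---|---|
| 8 unchanged, new pain of 2 | 8 | (8+2)/2 = 5 | -3 | 0 |
| 3 unchanged, new pain of 8 | 3 | (3+8)/2 = 5.5 | +2.5 | 0 |
| 8 and 2; the 2 resolves and is dropped | 5 | 8 | +3 | (8+0)/2 - 5 = -1 |
| 8 and 2; the 2 resolves, stays listed, scored 0 | 5 | (8+0)/2 = 4 | -1 | -1 |
| 8 and 2; the 8 resolves and is dropped | 5 | 2 | -3 | (0+2)/2 - 5 = -4 |
| 5 and 5; one resolves and is dropped | 5 | 5 | 0 | (5+0)/2 - 5 = -2.5 |
| 8 and 2; the 2 eases to 1 | 5 | (8+1)/2 = 4.5 | -0.5 | -0.5 |
| Single 6 resolves, opening question No | 6 | none | none | -6 |
| Single 6 resolves, stays listed, scored 0 | 6 | 0 | -6 | -6 |

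**Range.** For two conditions with integer scores a > b from 1 to 10, dropping the lower one gives a spurious worsening of (a - b)/2, from (2-1)/2 = +0.5 to (10-1)/2 = +4.5. For one condition scored a and a new one scored x with 1 ≤ x < a, the spurious improvement is (x - a)/2, from -0.5 to -4.5.

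**Loss from the analysis.** In Study Period III the only scheduled post-baseline assessment is Visit 7, or early termination instead. A patient whose opening answer there is No has nothing to average, so the at-least-one-postbaseline requirement is not met and the patient leaves the ANCOVA. The same patient can still enter the Study Period III/IV MMRM if scored at Visit 10 or 16.

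**The case against.** The strongest reply is that the form has its own answer for relief. The third item offers 0 for no pain in the past week, so a condition can stay listed with no current pain. Both relief cases are then scored correctly (-1 and -6 in the table). A reader might infer that relief always scores as worsening, or that complete relief always yields no score. The documents do not support either: both need the site to drop the condition or answer No. What stands is that the SAP does not say which recording applies. The opening question is in the present tense and skips the score when answered No. The same complete relief of a single pain of 6 can therefore be recorded as -6 or as missing.

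A reader might also infer that partial relief of a milder pain is scored as worse. That is wrong: any easing of a condition still reported lowers the mean.

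On new conditions, it can be said that an AE number may simply label a pain already present at baseline, and that a new pain above the existing mean scores as worsening. Both are true. But Protocol 8.2 has new conditions recorded as AEs, and nothing in SAP 5.4.2.2 keeps them out of the average.

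The analysis of conditions above the 15% threshold is unaffected by new pains. It leaves the averaged endpoint as it is, and it also gives no value to a condition that is no longer reported.

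**Conclusion.** The point holds as a gap in the derivation rule. The new-pain artefact follows from the text however resolved pains are recorded, provided the new score is below the patient's existing mean. The two relief artefacts are possible but not certain: they depend on a condition being dropped or on a No to the opening question.

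For one patient the error can be several points on a 0-10 scale and can reverse the sign. For the treatment comparison the size is unknown, because the documents give no rates of new or resolved conditions and do not say how sites record resolution. A reader might infer a definite bias against the drug. Suppose 20% of drug and 10% of placebo patients, each with a single pain of 6, resolve and the rest do not change. The difference is -6 × (0.20 - 0.10) = -0.6 if resolvers are scored 0, and 0 if all of them are missing. Those rates are assumptions, and new mild pains would favour whichever arm had more of them, so no net direction can be claimed.

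The consequence is limited to a tertiary, exploratory endpoint without multiplicity adjustment.

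**What to change.** Amend SAP 5.4.2.2, before treatment codes are opened to the study team, to say:

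1. The score is defined on the conditions reported at Visit 3, linked across visits by AE or medical history number.
2. At later visits, average those same conditions. Enter 0 where the assessment was completed and the condition is no longer present, including when the opening question is answered No. Set the score to missing only where the assessment was not done.
3. Summarise conditions first reported after Visit 3 separately, by treatment group.

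The downside is that a condition left off by oversight would be scored 0 and look like benefit. A sensitivity analysis should therefore treat unlisted baseline conditions as missing when the opening question is answered Yes. Linkage also needs a check: Protocol 8.2 has changes in pre-existing conditions recorded as AEs, so one condition could carry different numbers at different visits.

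The cost is a few sentences of SAP text and some programming. The identifiers and scores are already collected, so no new data are needed.

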5.4.3. Quality of Life and Other Questionnaires

5.4.3.1. Migraine Specific Quality of Life (MSQ) v2.1

Migraine Specific Quality of Life (MSQ) v2.1 consists of 14 questions. The questions measure the impact of migraine on health-related quality of life across 3 domains: 1) Role Function-Restrictive (7 questions), examines the degree to which performance of daily activities is limited by migraine; 2) Role Function-Preventive (4 questions), examines the degree to which performance of daily activities is prevented by migraine; 3) Emotional Function (3 questions), examines feelings of frustration and helplessness due to migraine.

Precoded item values and final item values for MSQ item responses are shown in Table CGAI.5.3. All item values range from 1 to 6. Final item values will be used for analysis with higher scores reflecting better quality of life.

Table CGAI.5.3. Item Values for Migraine Specific Quality of Life (MSQ) Item Responses

Response Categories	Precoded Item Value	Final Item Value
None of the time	1	6
A little bit of the time	2	5
Some of the time	3	4
A good bit of the time	4	3
Most of the time	5	2
All of the time	6	1

Questions 1 to 7 of the questionnaire will be grouped together as Role Function-Restrictive domain, questions 8 to 11 as Role Function-Preventive domain and questions 12 to 14 as the Emotional Function domain.

No imputation for missing values is necessary because the MSQ was collected using patient direct data entry on an electronic device which did not allow patients to skip items. Patients either completed the scale in its entirety or not at all.

The raw score of each domain will be calculated as the sum of the raw scores of each question in that domain, using imputed scores where applicable. Should it be the case that the number of missing responses was more than half the questions in that domain, meaning that imputation of missing scores will not be done, the raw score for that domain will not be calculated, hence missing.

The raw scores of each domain and the total score will be transformed to a 0 to 100 scale using the following formulae:

• Role Function-Restrictive (range of 7 to 42):

$$\frac{(\text{raw score} - 7)x100}{35}$$

• Role Function-Preventive (range of 4 to 24):

$$\frac{(\text{raw score} - 4) \times 100}{20}$$

• Emotional Function (range of 3 to 18):

$$\frac{(\text{raw score} - 3) \times 100}{15}$$

• Total Score (range of 14 to 84):

$$\frac{(\text{raw total score} - 14)x100}{70}$$

If any of the Role Function-Restrictive, Role Function-Preventive or Emotional Function domain is missing, then the total score will be missing, otherwise, the total score will be calculated as the sum of Role Function-Restrictive, Role Function-Preventive, and Emotional Function domain scores.

Responders in Role Function-Restrictive will be derived as outlined in 'Statistical Analysis Plan for Psychometric Properties of the MSQv2.1 Role Function-Restrictive Domain'.

5.4.3.2. MIDAS (Migraine Disability Assessment) Questionnaire

The Migraine Disability Assessment questionnaire (MIDAS) consists of 5 questions (Q1-Q5) and 2 additional questions (A and B). The questionnaire measures the impact that migraine headaches have on migraineurs' life, including days of work or school missed, days with productivity at work or school reduced to half or more, days with household work missed, days with productivity in household work reduced to half or more, and days missed family / so cial / leisure activities. Each question is answered as a number of days during the past 3 months of assessment, ranging from 0 to 90. The answers to all 5 questions will be added up to a total MIDAS score. No imputation for missing values is necessary because the MIDAS was collected using patient direct data entry on an electronic device which did not allow patients to skip items. Patients either completed the scale in its entirety or not at all.

The MIDAS responders are defined as patients with >50% improvement in the total MIDAS score.

The total MIDAS score, the raw score of each question, and the indicator of MIDAS responders will be used as analysis values.

5.4.3.3. Health Care Resource Utilization (HCRU) and Employment Status

Health Care Resource Utilization (HCRU) will be solicited by study personnel while documenting patient responses. Data to be collected include whether patients have hospital emergency room (ER) visits, overnight hospital stays, and other visits with healthcare professional, and, if yes, the numbers of above visits, as well as the numbers of above visits that are related to migraine headaches. Visits associated with their participation in the clinical trial should not be included in the responses. A question on employment status is also solicited, given the correlation and potential confounding with health outcomes measures.

At the baseline visit, these questions will be asked for the time frame of past 6 months. At postbaseline visits, the questions will be asked for the time from last visit to current visit.

Health Care Resource Utilization data will be analyzed at every 3-month interval. Baseline 3 months value will be derived as the baseline number divided by 2. Data from monthly Visit 5 to Visit 16 will be added for every 3 months. If missing data occur in more than 2 monthly visits, the 3-month period will have a missing data point.

If there is at least 1 non-missing data for HCRU for the patient, then all the other missing HCRU data for the same patients will be imputed as 0.

Data from the 3-month double-blind period will be analyzed relative to 3-month baseline data. Data from the entire 12-month treatment period (double-blind plus open-label periods) will also be analyzed in 3-month increments relative to the 3-month baseline data.

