8.9. Health Economics

Health economic, disability and quality of life assessments of LY2951742 in patients with migraine will be based on the following scales:

Migraine Disability Assessment Scale (MIDAS): The MIDAS was designed to quantify headache-related disability over a 3-month period. This instrument consists of five items that reflect the number of days reported as missing, or with reduced productivity at work or home and social events; higher values are indicative of more disability (Stewart 1999; Stewart 2001). This instrument is considered highly reliable and valid; and is correlated with clinical judgment regarding the need for medical care (Stewart 1999; Stewart 2001).

Migraine-Specific Quality of Life questionnaire (MSQ v2.1): The MSQ v2.1 is a self-administered health status instrument, and was developed to address physical and emotional limitations of specific concern to individuals suffering from migraine headaches. The instrument consists of 14 items that address 3 domains: (1) Role Function-Restrictive; (2) Role Function-Preventive; and, (3) Emotional Function (Jhingran 1998). The instrument was designed with a 4-week recall period, and is considered reliable, valid and sensitive to change in migraine (Jhingran 1998; Rendas-Baum 2013). Clinically meaningful differences for each domain have been established and are widely used in the literature.

Health Care Resource Utilization (HCRU) and Employment Status: The HCRU will be solicited by study personnel while documenting patient responses. The HCRU consists of 3 questions, asking about hospital emergency room visits, overnight stays in a hospital, and any other visits with a healthcare professional that occurred since their last study visit. Patients are also specifically asked about the number of health care events that are related to migraine headaches, outside of visits associated with their participation in the clinical trial. The baseline visit will include the same questions, however with the frame of reference being over the last 6 months. A question on employment status is also solicited, given the correlation and potential confounding with health outcomes measures.

9. Statistical Considerations and Data Analysis

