5.5.11. Quality-of-Life (QoL) Analyses

The mean change from baseline to each postbaseline visit for SP III and SP III/IV/V for MSQ (including Role Function-Restrictive, Role Function-Preventive, Emotional Function, and total score), as defined in Section 5.4.3 will be evaluated using MMRM as described in Section 5.5.10.1.

Mean change from baseline to LOCF endpoint in the 3-month treatment phase for above quality of life measures will be evaluated using the ANCOVA model as described in Section 5.5.1.1.

The change from baseline to Month 3 score in MIDAS (item scores and total score) will be evaluated using the ANCOVA model as described in Section 5.5.1.1. The mean change from baseline to each postbaseline visit for SP III/IV and for SP III/IV/V for MIDAS (item scores and total score) will be evaluated using MMRM as described in Section 5.5.10.1.

Indicators of the MSQ Role Function Restrictive domain responders and MIDAS responders will be analyzed using GLIMMIX (as described in Section 5.5.10.3). Threshold for MSQ Role Function Restrictive domain response will be derived as outlined in "Statistical Analysis Plan for Psychometric Properties of the MSQv2.1 Role Function-Restrictive Domain". The threshold for MIDAS response will be a 50% improvement from baseline in MIDAS total score.

For the HCRU, the following measures will be analyzed:

- number of hospital emergency room (ER) visits
- number of overnight hospital stays
- number of other visits with healthcare professional
- number of hospital ER visits related to migraine headache
- number of overnight hospital stays related to migraine headache
- number of other visits with healthcare professional related to migraine headache

All of the above measures for the HCRU will be analyzed with a repeated measures negative binomial regression analysis fitted with SAS PROC GLIMMIX. The model includes pooled country, month, baseline medication overuse (yes versus no), concurrent prophylaxis use (yes versus no) and treatment-by-month interaction, as well as the continuous fixed covariates of

baseline and baseline-by-month interaction, log (number of actual number of days within every 3 month/90) as the offset in the model. In case of non-convergence, pooled country and/or baseline-by-month interaction may not be included in the model.

Employment status at each visit will be summarized separately for each treatment groups.

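### The HCRU zero rule in SAP 5.4.3.3, as worded, overrides the missing-period rule and scores unobserved time, mainly later quarters after dropout or non-entry to open-label, as no health care use

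*SAP*

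**What the plan says.** SAP 5.4.3.3 builds quarterly counts from monthly reports: "Data from monthly Visit 5 to Visit 16 will be added for every 3 months". Visits 5 to 16 are 12 visits, so there are four quarters: one double-blind and three open-label. For baseline, "Baseline 3 months value will be derived as the baseline number divided by 2", the question there covering six months.

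Two missing-data rules follow in successive paragraphs:

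- Period rule: "If missing data occur in more than 2 monthly visits, the 3-month period will have a missing data point".
- Zero rule: the trigger is a single HCRU value on record, and the consequence is stated as "then all the other missing HCRU data for the same patients will be imputed as 0".

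The zero rule is worded per patient, with no limit by visit, by quarter or by reason for the gap.

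On recall, the SAP states: "At postbaseline visits, the questions will be asked for the time from last visit to current visit". Protocol 8.9 agrees, asking about emergency visits, hospital stays and "any other visits with a healthcare professional that occurred since their last study visit".

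SAP 5.5.11 analyses the counts with a repeated measures negative binomial model that has "log (number of actual number of days within every 3 month/90) as the offset in the model". Neither document says which days are the actual ones.

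**The concern.** A zero is a claim that the patient used no care. That is sound when the patient was asked and said no, or when a later report covers the gap. It is not sound for time on which nobody reported.

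The sets analysed keep such patients in. In SAP Table CGAI.5.4, the combined Study Period III/IV quality-of-life set needs only a baseline and one later value. Open-label entry is optional (Protocol 4.1). A patient who completes Month 3 and stops there could therefore be recorded as using no health care for nine months.

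Zeros can even sit beside contrary data. Patients who discontinue go to the post-treatment phase, and Protocol Appendix 2 schedules HCRU at Visits 17 and 18 and at early termination, but the SAP sums only Visits 5 to 16.

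The plan treats its other counts differently. SAP 5.4.1 scales diary counts to the days observed and sets poorly completed months to missing. At stake are the level of HCRU and its trend over 12 months, where attrition alone could look like falling use.

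**Working it through.** The plan gives no HCRU figure to reproduce. The check compares the rules case by case and then sizes the effect.

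**1. The two rules side by side**

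| Patient | Period rule | Zero rule as worded |
|---|---|---|
| Baseline only, no Visit 5–7 report | Double-blind quarter missing | 0, but excluded if a later value is required |
| Visit 5 report, then dropout | Quarter kept (2 of 3 missing) | Visits 6 and 7 set to 0: no conflict, but unobserved time scored 0 |
| Visit 6 missed, Visit 7 completed | Quarter kept | Visit 6 set to 0: harmless, as Visit 7 recall covers the gap |
| Completes Month 3, does not enter open-label | Three quarters missing | Three quarters set to 0: conflict |
| Last report at Visit 10 | Last two quarters missing | Last two quarters set to 0: conflict |

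**2. Double-blind quarter, calendar-day offset (90 days for everyone)**

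Input: discontinuation share d = 0.15 (SAP 5.2).

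Assumptions: the same true rate for all patients; a dropout's last completed monthly visit equally likely to be number 0, 1 or 2 of 3; no early-termination report counted.

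- Mean observed share among dropouts: (0 + 1/3 + 2/3)/3 = 1/3.
- Baseline-only patients kept: recorded/true = 1 − 2d/3 = 1 − 0.10 = 0.90.
- Baseline-only patients (share d/3) excluded: (1 − 2d/3)/(1 − d/3) = (3 − 2d)/(3 − d) = 2.70/2.85 = 0.947.
- For d from 5% to 25%: 0.967 to 0.833 if kept, 0.983 to 0.909 if excluded.
- Variant in which every dropout reports at early termination and leaving dates are spread evenly: 1 − 0.15 × 0.5 = 0.925.

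**3. Double-blind quarter, offset equal to days covered by reports**

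Events and exposure now stop together, so recorded/true = 1.00 for partly observed quarters. A simulation of 400,000 patients with Poisson counts gave 0.901 (kept), 0.948 (excluded) and 1.001 (observed days).

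**4. Later quarters**

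Let D be the share of analysed patients wholly missing in a quarter.

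- Calendar days: recorded/true = 1 − D, so 0.85 at D = 15%, 0.70 at 30% and 0.60 at 40%. The documents do not give D. Only completers of the double-blind phase may enter open-label, so D is at least the share who left before Month 3.
- Days covered by reports: the offset is log(0/90), which is undefined. The record either drops out of the fit, so the imputed zero has no use, or needs an invented positive exposure, which makes it a false zero.

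**5. Between arms, equal true rates, calendar days**

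Dropout by arm is assumed; the documents give only the overall 15%.

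- 20% vs 10%: 0.9286/0.9655 = 0.962 (excluded), or 0.8667/0.9333 = 0.929 (kept).
- 15% vs 15%: 1.00.

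**The case against.** The strongest defence has four parts.

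**Scope.** Within one 3-month period, more than two visits missing means all three, which is the exact complement of at least one non-missing. If the zero rule was meant within a period, the rules fit together. This is plausible, but the SAP names the patient as the unit, and a programmer following the text would apply it that way. Even on this reading, time after the last report within a quarter is scored 0.

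**Form coding.** SAP 5.4.3.3 describes a gated form: whether there were visits and, if so, how many. Blank counts after a no should be zero. That is correct, and the fix keeps it, but the rule is not limited to that case.

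**Population.** A reader might infer that a baseline value alone brings a patient into the double-blind analysis as a zero. The documents do not support that. Protocol 9.2 requires a baseline and a postbaseline value for change analyses, and Table CGAI.5.4 sets the same condition for Study Period III efficacy. The table's quality-of-life row for that period appears to share the cell. This largely removes the conflict in the double-blind phase, but not in later quarters.

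**Offset.** A reader might also infer that utilization is certainly biased low. It is not certain: if the actual days are those covered by reports, partly observed quarters are unbiased. The SAP does not say so, and no definition of the days makes a zero valid in a wholly missing quarter.

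**Conclusion.** The concern holds in a limited form. As worded, the zero rule overrides the period rule, mainly in the three open-label quarters of the 12-month series.

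The size is conditional. With a calendar-day offset, double-blind use is understated by about 5% at 15% dropout among patients with at least one postbaseline report, and by up to about 10% if baseline-only patients are kept. A later quarter is understated by the share wholly missing. These figures rest on a constant rate and evenly spread last visits. With an offset of days covered by reports, only the wholly missing quarters remain a problem.

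It is tempting to conclude that the rule favours the arm with more dropout and hence the drug. The documents give no dropout by arm, so the size and direction of any between-arm bias are unknown, and with equal dropout there is none.

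HCRU is an other-secondary endpoint without multiplicity control. Primary and key secondary results are unaffected.

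**What to change.** Replace the blanket zero sentence in SAP 5.4.3.3 and define the offset in 5.5.11:

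- Set a count to 0 only if it is blank because the gate question was answered no, or if a missed visit is followed in the same 3-month period by a completed HCRU report whose recall covers the gap. A visit attended without HCRU does not qualify, because the next recall starts from that visit.
- Leave missing all wholly unobserved periods and all time after the last HCRU report.
- Use early-termination HCRU data up to that visit.
- Define the offset as log(days covered by completed HCRU reports / 90). State where Visit 5 recall begins: Visit 4 is a study visit without HCRU (Protocol Appendix 2), so read literally Visit 5 covers only the time since Visit 4.

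The cost is SAP wording, a small change to one derivation, and slightly fewer patient-periods in an other-secondary analysis.
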